5.2 Contraception Recommendations

Contraception Requirements for Females

Subjects must follow the following contraceptive guidelines as specified:

- Females, Nonchildbearing Potential
 - Females do not need to use birth control during or following study drug treatment if considered of nonchildbearing potential due to meeting any of the following criteria:
 1. Premenopausal female with permanent sterility or permanent infertility due to one of the following:
 - [REDACTED]
 - [REDACTED]
 2. Postmenopausal female
 - [REDACTED]
 - [REDACTED]
- Females, of Childbearing Potential
 - Review and document pregnancy avoidance recommendations with females of childbearing potential
 - Females of childbearing potential must avoid pregnancy during the study.
 - Females must commit to one of the following methods of birth control:
 - [REDACTED]
 - [REDACTED]

Term	Percentage
GMOs	85%
Organic	75%
Natural	70%
Artificial	65%
Organic	60%
Natural	55%
Artificial	50%
Organic	45%
Natural	40%
Artificial	35%

Contraception recommendations related to use of concomitant therapies prescribed should be based on the local label.

5.3 Prohibited Medications and Therapy

The decision to administer any prohibited medication/treatment during the study period is done with the safety of the subject as the primary consideration. Additionally, the medication/treatment listed below are prohibitive due to the potential confounding impact to efficacy assessment and not due to any potential safety risk to the subject. When possible, the sponsor is to be notified before the prohibited medication/treatment is administered.

Prohibited treatments and procedures include, but are not limited to:

Term	Percentage
Climate change	85%
Global warming	95%
Green energy	80%
Carbon footprint	70%
Sustainable development	98%
Renewable energy	85%
Emissions reduction	75%
Carbon tax	60%
Green economy	80%

Site staff must notify the sponsor if a subject is administered or has taken any concomitant medications/procedures not permitted by the protocol.

5.4 Prior and Concomitant Therapy

Any medication or vaccine [REDACTED]

[REDACTED] that the subject is receiving at the time of enrollment or receives during the study must be recorded from 30 days prior to study drug administration through study exit. See below for details on special handling for the COVID-19 vaccine.

The use of any medication during the study [REDACTED]

[REDACTED] is to be recorded on the subject's electronic case report form (eCRF) at each visit along with the reason the medication is taken, dates of use, and dosing regimen. Concurrent procedures will also be collected at each visit. Concomitant medications and concurrent procedures will be tabulated and listed.

Non-live vaccines may be used during screening or treatment periods, if not contraindicated or medically inappropriate. [REDACTED]

[REDACTED]
Any questions regarding concomitant or prior therapy should be raised to the AbbVie nonemergency contact. Information regarding potential drug interactions with BOTOX are in the BOTOX Investigator's Brochure.

[COVID-19 Pandemic-Related Vaccination Guidance](#)

Given the ongoing COVID-19 pandemic, selected non-live vaccines (e.g., messenger RNA, non-replicating viral vector, protein subunit, etc.) to prevent SARS-CoV-2 infection may be administered during screening, the treatment period, or follow-up, as long as components of the vaccine are not contraindicated.

The decision to receive a locally available vaccine should be based on local guidance and an individual discussion between the treating physician and the subject.

[figure not shown]
Any SARS-CoV-2 vaccine information must be documented on the COVID-19 vaccine eCRF. Refer to the Operations Manual for instructions on reporting any AEs associated with the COVID-19 vaccine.

5.5 Withdrawal of Subjects and Discontinuation of Study

A subject may voluntarily withdraw or be withdrawn from the study at any time.

For subjects to be considered lost to follow-up, reasonable attempts must be made to obtain information on the subject's final status.

AbbVie may terminate this study prematurely, either in its entirety or at any site. The investigator may also stop the study at his/her site if he/she has safety concerns. If AbbVie terminates the study for safety reasons, AbbVie will promptly notify the investigator.

Term	Percentage
GMOs	~75%
Organic	~95%
Natural	~95%
Artificial	~15%

COVID-19 Pandemic-Related Acceptable Protocol Modification

During the COVID-19 pandemic, it may be necessary to employ mitigation strategies to enable the investigator to ensure subject safety and continuity of care. [REDACTED]

The investigator should contact the AbbVie nonemergency contact before discontinuing a subject from the study for a reason other than described in the protocol to ensure all acceptable mitigation steps have been explored.

5.6 Follow-Up After Subject Discontinuation of Study Drug or from Study

To minimize missing data for safety and efficacy assessments, subjects should continue to be followed for all regularly scheduled visits, unless subjects have decided to discontinue the study participation entirely.

If a subject prematurely discontinues study participation (withdrawal of informed consent), the procedures outlined for the Premature Discontinuation visit should be completed as soon as possible.

[REDACTED]

[REDACTED]

5.7 Study Drug

BOTOX and matching placebo will be packaged in vials with quantities sufficient to accommodate study design (Table 3). Study drug provided by AbbVie should not be substituted or alternately sourced unless otherwise directed by AbbVie.

[REDACTED]

[REDACTED]

Study drug will only be used for the conduct of this study.

Sites are responsible for maintaining the investigational study drug and devices according to the storage conditions specified.

[REDACTED]

[REDACTED]

[REDACTED]

Dosing will be determined based on the baseline C-APPS score on Day 1.

[REDACTED]

[figure not shown]
[figure not shown]
[REDACTED]

[REDACTED]

Table 3. Study Formulations and Dilution Instructions

Investigational Medicinal Product	BOTOX	Placebo
Dose Formulation	BOTOX (botulinum toxin type A) purified neurotoxin complex [REDACTED]	[REDACTED]
Dilution Instructions	[REDACTED]	[REDACTED]
Packaging and Labeling	[REDACTED]	[REDACTED]
Storage	[REDACTED]	[REDACTED]
Manufacturer	Allergan	

[figure not shown]

5.8 Randomization/Drug Assignment

All subjects will be assigned a unique identification number by the IRT at the screening visit. For subjects who rescreen, the screening number assigned by the IRT at the initial screening visit should be used. The IRT will assign a randomization number that will encode the subject's treatment group assignment according to the randomization schedule.

All AbbVie personnel with direct oversight of the conduct and management of the trial (with the exception of AbbVie Drug Supply Management Team), the investigator, study site personnel, and the subject will remain blinded to each subject's treatment throughout the study. The IRT will provide access to unblinded subject treatment information in the case of a medical emergency.

At each study site, designated staff member(s) will serve as the Independent Drug Reconstitutor (IDR). This person will be unblinded and will be responsible for study drug preparation and documentation.

Blinding is critical to the integrity of the clinical trial. The IRT will be programmed with blind-breaking instructions.

the investigator is to make every effort to contact AbbVie prior to unblinding a subject's study drug assignment unless this could delay emergency treatment of the subject.

The date and reason that the blind was broken must be recorded in the source documentation and case report form, as applicable.

5.9 Protocol Deviations

AbbVie does not allow intentional/prospective deviations from the protocol except when necessary to eliminate an immediate hazard to study subjects.

5.10 Data Monitoring Committee

A data monitoring committee is not planned for this study.

6 SAFETY CONSIDERATIONS

6.1 Complaints and Adverse Events

Complaints

A complaint is any written, electronic, or oral communication that alleges deficiencies related to the physical characteristics, identity, quality, purity, potency, durability, reliability, safety, effectiveness, or performance of a product/device. Complaints associated with any component of this investigational product must be reported to AbbVie.

Product Complaint

A product complaint is any complaint related to the biologic or drug component of the product or to the medical device component(s).

Product complaints concerning the investigational product and/or device must be reported to AbbVie

Reporting will be done via electronic data capture (EDC).

A back-up paper form

will be provided for reporting complaints related to unassigned product or in the event of an EDC system issue.

All follow-up information is to be reported to the sponsor (or an authorized representative) and documented in source as required by the sponsor. Product complaints associated with AEs will be reported in the study summary. All other complaints will be monitored on an ongoing basis. Product complaints occurring during the study will be followed up to a satisfactory conclusion.

Medical Complaints/Adverse Events and Serious Adverse Events

An AE is defined as any untoward medical occurrence in a subject or clinical investigation subject administered a pharmaceutical product and which does not necessarily have a causal relationship with this treatment.

The investigators will monitor each subject for clinical evidence of AEs on a routine basis throughout the study. All AEs will be followed to a satisfactory conclusion.

If an AE, whether associated with study drug or not, meets any of the following criteria, it is to be reported to AbbVie clinical pharmacovigilance as an SAE.

[figure not shown]
■ [REDACTED]	
■ [REDACTED]	
■ [REDACTED]	
Death of Subject	An event that results in the death of a subject.
Life-Threatening	An event that, in the opinion of the investigator, would have resulted in immediate fatality if medical intervention had not been taken. This does not include an event that would have been fatal if it had occurred in a more severe form.
Hospitalization or Prolongation of Hospitalization	An event that results in an admission to the hospital for any length of time or prolongs the subject's hospital stay. This does not include an emergency room visit or admission to an outpatient facility.
Congenital Anomaly	An anomaly detected at or after birth, or any anomaly that results in fetal loss.
Persistent or Significant Disability/Incapacity	An event that results in a condition that substantially interferes with the activities of daily living of a study subject.

**Important Medical Event
Requiring Medical or Surgical
Intervention to Prevent
Serious Outcome**

An important medical event that may not be immediately life-threatening or result in death or hospitalization, but based on medical judgment may jeopardize the subject and may require medical or surgical intervention to prevent any of the outcomes listed above

All AEs reported from the time of study drug administration

 will be collected, whether solicited or spontaneously reported by the subject. In addition, study procedure-related serious and nonserious AEs will be collected from the time the subject signs the study-specific informed consent.

The following definitions will be used for serious adverse reaction (SAR) and suspected unexpected serious adverse reaction (SUSAR):

SAR	Defined as all noxious and unintended responses to an investigational medicinal product related to any dose administered that result in an SAE as defined above.
SUSAR	Refers to individual SAE case reports from clinical trials where a causal relationship between the SAE and the investigational medicinal product was suspected by either the sponsor or the investigator, is unexpected (not listed in the applicable Reference Safety Information), and meets one of the above serious criteria.

AbbVie will be responsible for SUSAR reporting for the investigational medicinal product in accordance with global and local requirements.

Adverse events will be monitored throughout the study to identify any of special interest that may indicate a trend or risk to subjects.

[REDACTED]
[REDACTED]
[REDACTED]
[REDACTED]
[REDACTED]
[REDACTED]

[REDACTED]
[REDACTED]
[REDACTED]

Upon identification and awareness of 1 or more of these events, the investigator must document and report the event by completing an AE eCRF, and must notify the AbbVie nonemergency contact and assigned clinical research associate by email or telephone call within 72 hours of awareness (if non-serious). The SAE form is not needed unless the AESI is serious. If the AESI meets SAE criteria (which are listed above), it must be reported per the sponsor's SAE reporting requirements described above [REDACTED].

Adverse Event Severity and Relationship to Study Drug

The investigator will use the following definitions to rate the severity of each AE:

Mild	The AE is transient and easily tolerated by the subject.
Moderate	The AE causes the subject discomfort and interrupts the subject's usual activities.
Severe	The AE causes considerable interference with the subject's usual activities and may be incapacitating or life threatening.

The investigator will use the following definitions to assess the relationship of the AE to the use of study drug:

Reasonable Possibility	After consideration of factors including timing of the event, biologic plausibility, clinical judgment, and potential alternative causes, there is sufficient evidence (information) to suggest a causal relationship.
No Reasonable Possibility	After consideration of factors including timing of the event, biologic plausibility, clinical judgment, and potential alternative causes, there is insufficient evidence (information) to suggest a causal relationship.

Pregnancy

While not an AE, pregnancy in a study subject must be reported to AbbVie within 24 hours after the site becomes aware of the pregnancy. [REDACTED]

The pregnancy outcome of an elective or spontaneous abortion, stillbirth, or congenital anomaly is considered an SAE and must be reported to AbbVie per the SAE reporting requirements described above.

Possible Distant Spread of Toxin

Possible distant spread of toxin (PDSOT) is defined as a possible pharmacologic effect of botulinum toxin at sites noncontiguous and distant from the site of injection. Utilizing a standardized methodology to assess for PDSOT, Medical Dictionary for Regulatory Activities PTs that may be associated with botulinum toxin effects have been prospectively identified [REDACTED]

7 STATISTICAL METHODS & DETERMINATION OF SAMPLE SIZE

7.1 Statistical and Analytical Plans

The statistical methods provided in this protocol will be focused on primary and secondary analyses. Complete and specific details of the statistical analysis will be described in the Statistical Analysis Plan.

7.2 Definition for Analysis Populations

The ITT population consists of all randomized subjects.

Baseline analyses and efficacy analyses for US FDA will be performed on the ITT population, consisting of all randomized subjects.

For EU regulatory agencies only, baseline analyses and efficacy analyses will be performed on the mITT populatio [REDACTED]

The Safety Analysis Set consists of all subjects who received at least 1 dose of study drug. All safety analyses will be performed with subjects analyzed by their actual treatment received. The Safety Analysis Set will be used for all safety analyses.

7.3 Handling Potential Intercurrent Events for the Primary and Secondary Endpoints

The primary composite endpoint for the FDA and the coprimary endpoint for the EU regulatory agencies (defined in Section 3.2) will be analyzed based on the ITT population and the mITT population, respectively, and the following methods will be used to address potential intercurrent events:

- Subjects who did not receive any dose of study drug but are randomized will still be included in the ITT population. [REDACTED]
- Subjects who are randomized but prematurely discontinued the study before assessment of the primary endpoints will be considered as part of the ITT population. [REDACTED]
- Subjects who die before assessment of the primary endpoint will count as though they hypothetically continued in the study.
- Subjects who are lost to follow-up and are missing data for the primary endpoint will count as though they hypothetically continued in the study.
- Subjects who are missing assessments or data due to the COVID-19 pandemic and are missing data for the primary composite or coprimary endpoints will count as though they hypothetically continued in the study.
- Subjects who are missing data for any other reason for the primary endpoint will count as though they hypothetically continued in the study.

The efficacy analysis of secondary endpoints (defined in Section 3.3) will be analyzed based on the same populations as above with similar methods for addressing potential intercurrent events.

Missing values will be imputed per the below.

Missing data will be imputed using the following methods for the efficacy analyses:

- Multiple Imputation: The Multiple Imputation approach will be used as a primary analysis for the primary endpoint, as well as for all secondary endpoints. For the primary endpoint (US: composite endpoint; EU: coprimary endpoints) and the primary measure through Day 120. [REDACTED]

- Non-responder Imputation (NRI): The NRI analysis will categorize any subject who does not have evaluation during a specific visit window as a nonresponder for that visit. The NRI will be one of the sensitivity analysis approaches in the analyses of categorical variables for efficacy.
- As Observed (AO): The AO analysis will not impute values for missing evaluations, and thus a subject who does not have an evaluation on a scheduled visit will be excluded from the AO analysis for that visit. AO will include all values collected in the study, and will be used for sensitivity analyses of efficacy endpoints.

7.4 Statistical Analyses for Efficacy

Summary and Analysis of the Primary Endpoints

Analysis of the primary endpoint will be conducted on the ITT population based on treatment as randomized for the US FDA analyses and on the mITT population based on treatment as randomized for the EU regulatory agencies.

US FDA: The composite responder endpoint for a Grade 1 or 2 (Minimal or Mild) and at least a 2-grade improvement will be analyzed using the CMH method [REDACTED]

EU regulatory agencies: In addition, the coprimary responder endpoints for at least a 2-grade improvement in the C-APPS and P-APPS separately will be analyzed using the CMH method [REDACTED]

The evaluation of the equality of the proportions of responders for the primary endpoint at Day 14 will be based on the CMH test stratified by baseline C-APPS score on Day 1 and by investigator site. A 2-sided p-value < 0.05 will be claimed as statistically significant. [REDACTED]

[REDACTED] The 95% CI for the treatment risk differences will be constructed using the normal approximation to the binary distribution.

Sensitivity analyses of the primary efficacy variables will be performed to establish their consistency and robustness as well as to further characterize the extent of subjects' responses. [REDACTED]

Summary and Analysis of Secondary Endpoints

Analysis of the secondary endpoints will be conducted on the ITT population based on treatment as randomized for the US FDA analyses and on the mITT population based on treatment as randomized for the EU regulatory agencies.

For the secondary endpoints, the proportion of responders will be analyzed using the CMH test [REDACTED]

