5 STUDY ACTIVITIES

5.1 Eligibility Criteria

Subjects must meet all of the eligibility criteria in order to be included in the study. Screen failures can occur during the screening period up to the Day 1 Visit. [REDACTED]

[REDACTED] Any attempt to rescreen a subject must only occur after agreement with the sponsor.

[REDACTED]

[REDACTED]

[REDACTED]

Anything other than a positive response to the questions below will result in screen failure.

Consent

- 1. Subjects must voluntarily **sign and date an informed consent**, approved by an independent ethics committee (IEC)/institutional review board (IRB), prior to the initiation of any screening or study-specific procedures
- 2. Are willing and able to comply with procedures required in this protocol

Demographics

- 3. Adult **male or female**, at least 18 years old at the time of signing the informed consent
- [REDACTED]

Condition

- [REDACTED]
- 6. Either moderate (Grade 3) or severe (Grade 4) platysma prominence [REDACTED] as determined at maximum contraction [REDACTED] by the investigator using the C-APPS
- 7. Either moderate (Grade 3) or severe (Grade 4) platysma prominence [REDACTED] as determined at maximum contraction [REDACTED] by the subject using the P-APPS
- [REDACTED]

Subject History

- ✓ 11. Good health as determined by medical history, physical examination, vital signs, and investigator's judgment
- ✓ 12. No abnormal variations and abnormal anatomical features in the lower face, neck, or décolletage area
- ✓ 13. No history of dermatological disease
- ✓
- ✓
- ✓
- ✓ 15. No medical condition that may put the subject at increased medical risk with exposure to BOTOX, including diagnosed myasthenia gravis, Eaton-Lambert syndrome, amyotrophic lateral sclerosis, or any other condition that might interfere with neuromuscular function
- ✓ 16. No lower facial and neck hair, scarring
- ✓ 17. No tattoos, jewelry, or clothing that cannot be removed, and that obscure the target area of interest
- ✓ 18. No history of body weight change [REDACTED] prior to screening or anticipated body weight change [REDACTED] during the study period
- ✓ 19. No known immunization or hypersensitivity to any botulinum toxin serotype
- ✓ 20. No history of an **allergic reaction** or significant sensitivity to constituents of the study drug (and its excipients) and/or other products in the same class
- ✓ 21. No history of clinically significant (per investigator's judgment) **drug or alcohol abuse** [REDACTED]

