2.3 Treatment Assignment and Blinding

Subjects will be randomized to BOTOX or placebo in a 1:1 ratio. Randomization will be stratified at each investigational site by baseline C-APPS on Day 1 [REDACTED]

[REDACTED] The same block will not be shared across sites or by baseline C-APPS.

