3.0 Endpoints

3.1 Primary Endpoints

For the FDA, the primary composite efficacy endpoint is achievement of Grade 1 or 2 (Minimal or Mild) and at least a 2-grade improvement from baseline based on both investigator's assessment using the C-APPS and subject's self-assessment using P-APPS at maximum contraction at Day 14, that is, Grade 1 or 2 with at least a 2-grade improvement on the C-APPS on Day 14 AND Grade 1 or 2 with at least a 2-grade improvement on the P-APPS on Day 14.

For EU regulatory agencies, the coprimary efficacy endpoints are the achievement of at least a 2-grade improvement from baseline based on the following: (1) investigator's assessment using C-APPS at maximum contraction at Day 14, and (2) subject's self-assessment using P-APPS at maximum contraction at Day 14.

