9.3 Primary Efficacy Endpoints and Analyses

9.3.1 Primary Efficacy Endpoints

Clinician Allergan Platysma Prominence Scale (C-APPS): The sponsor developed the C-APPS as a clinician's assessment tool for evaluation of platysma prominence at maximum contraction. [REDACTED]

[REDACTED]

[REDACTED]

[REDACTED]

[REDACTED]

Prior to enrolling subjects, investigators (or sub-investigators when applicable) will be trained in grading platysma prominence severity using the C-APPS.

The C-APPS is to be performed by the same trained and qualified (MD/DO) evaluator throughout the study [REDACTED]

[REDACTED]

[REDACTED]

[REDACTED]

Platysma prominence [REDACTED] will be assessed live, independently, at maximum contraction by the investigator using the C-APPS (1 = Minimal, 2 = Mild, 3 = Moderate, 4 = Severe, 5 = Extreme).

There are no COVID-19 protocol modifications for the C-APPS procedure. If a site visit is missed at which this assessment was planned, the assessment will be skipped for that timepoint.

Participant Allergan Platysma Prominence Scale (P-APPS): The P-APPS has been developed as a subject self-assessment tool for evaluation of platysma prominence at maximum contraction [REDACTED] [REDACTED]

[REDACTED]

Subjects will use the P-APPS (1 = Minimal, 2 = Mild, 3 = Moderate, 4 = Severe, 5 = Extreme) [REDACTED] to self-assess the severity of their left and right platysma prominence at maximum contraction (left and right ratings captured separately).

There are no COVID-19 protocol modifications for the P-APPS procedure. If a site visit is missed at which this assessment was planned, the assessment will be skipped for that timepoint.

[REDACTED]

[REDACTED]

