9.3.3 Sensitivity and Supplementary Analyses of the Primary Efficacy Endpoints

Sensitivity analyses of the primary efficacy variables will be performed to establish their consistency and robustness as well as to further characterize the extent of subjects' responses. As-observed data analysis, as well as missing as non-responder (using NRI) analysis [REDACTED]

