9.6 Efficacy Subgroup Analyses

Efficacy analyses for the primary composite and coprimary endpoints will be performed by subgroups of sex, age group [REDACTED], BMI [REDACTED] race [REDACTED] ethnicity [REDACTED] region [REDACTED] and baseline C-APPS at maximum contraction [REDACTED]

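### Does the EU P-APPS coprimary need an analysis adjusted for baseline P-APPS grade, as well as for baseline C-APPS and site?

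*Protocol*

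**What the plan says.** Protocol 7.4 gives one readable stratification for the Day 14 primary test: a "CMH test stratified by baseline C-APPS score on Day 1 and by investigator site". SAP 2.3 names the same two factors for allocation: "Randomization will be stratified at each investigational site by baseline C-APPS on Day 1". The sentence on the EU coprimaries breaks off in a redaction, so applying this stratification to them is the natural reading but cannot be confirmed.

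For the EU, SAP 3.1 states that "the coprimary efficacy endpoints are the achievement of at least a 2-grade improvement from baseline", once on C-APPS and once on P-APPS. SAP 9.3.1 grades P-APPS from 1 (Minimal) to 5 (Extreme), with "left and right ratings captured separately". Protocol 5.1 has this entry criterion on the self-rating: "7. Either moderate (Grade 3) or severe (Grade 4) platysma prominence".

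Baseline P-APPS grade is tabulated by arm for the ITT and mITT populations (SAP 7.0 and 7.1). The readable subgroup list in SAP 9.6 closes with "and baseline C-APPS at maximum contraction" and does not name P-APPS. The readable sensitivity analyses in SAP 9.3.3 are "As-observed data analysis, as well as missing as non-responder (using NRI) analysis", which deal with missing data. Text is blacked out in or after each of these analysis descriptions, in the Statistical Summary cells of Table 1 in both documents, and in SAP 9.1; SAP 9.5 has no readable content.

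**The concern.** The two EU coprimaries have equal standing but seem to be treated unequally. A 2-grade improvement is harder from Grade 3, where the subject must reach the bottom of the scale, than from Grade 4. For C-APPS, the plan covers this three times: in randomisation, in the CMH strata and in the subgroups. For P-APPS, no readable stratum, covariate or subgroup uses the subject's own baseline.

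If one arm happened to hold more subjects at P-APPS Grade 4, that arm would have an easier target. The baseline table would show the imbalance, and no readable analysis would say how far it had moved the EU result. Some precision might also be lost.

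**Working it through.** **1. The responder bar.** 3 − 2 = 1, so a Grade 3 subject must reach Grade 1. 4 − 2 = 2, so a Grade 4 subject must reach Grade 2 or 1. The premise is right, provided that one grade per subject is formed from the two sides; the combining rule is not readable.

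**2. The plan's own figures.** 400 × (1 − 0.10) = 360 reproduces the FDA number. The power above 99% with 180 subjects for the EU cannot be reproduced, because the assumed rates are redacted. It can be turned round. For a two-group chi-square test at two-sided 0.05, the smallest difference giving 99% power is:

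| Placebo rate | 90 per arm | 180 per arm |
|---|---|---|
| 1% | 19.2 points | 11.0 points |
| 5% | 23.2 points | 14.7 points |
| 10% | 26.3 points | 17.4 points |

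Whether 180 is the total or per arm is not readable. The total (90 per arm) is the natural reading beside 360 subjects.

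**3. How large chance imbalance can be.** Let q be the share at P-APPS Grade 4, n the number per arm and φ the correlation of baseline C-APPS with P-APPS. With C-APPS balanced by design, the SD of the between-arm difference in that share is √(2q(1−q)/n) × √(1−φ²). At n = 90, q = 0.5, φ = 0 it is √(0.5/90) = 0.0745, so the 95% range is ±1.96 × 7.45 = ±14.6 points. At φ = 0.6 it shrinks to ±11.7. At n = 180 the two values are ±10.3 and ±8.3. Both q and φ are assumptions.

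**4. How far imbalance moves the result.** The shift is the imbalance times the average over arms of the response gap between grades. The documents give no rates by grade, so four settings were assumed (Grade 3/Grade 4):

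| Setting | BOTOX | Placebo | Average gap | Shift per 10 points of imbalance |
|---|---|---|---|---|
| A, strong | 20/50% | 1/5% | (30+4)/2 = 17 | 1.7 |
| B, strong | 25/60% | 5/15% | (35+10)/2 = 22.5 | 2.25 |
| C, mild | 30/45% | 3/6% | (15+3)/2 = 9 | 0.9 |
| D, none | 38/38% | 5/5% | 0 | 0 |

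A simulation (3,000 trials per cell, site and C-APPS strata, blocks of 4, C/P agreement of 60% to 90%) agrees: 1.0 to 2.5 points in A and B, 0.4 to 1.1 in C, about 0 in D. With half of subjects at Grade 4, the SD of the planned difference was 3.8 to 4.5 points at N = 360 and 5.4 to 6.4 at N = 180.

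**5. Imbalance is already inside the standard error.** Take N = 180 and 60% agreement. With half of subjects at Grade 4, φ = 2 × 0.6 − 1 = 0.2, and the SD of the imbalance is 0.0745 × √0.96 = 0.073. It contributes 17 × 0.073 = 1.24 points (A) or 22.5 × 0.073 = 1.64 points (B) to an SD of 5.4 to 6.4. As a share of variance that is 1.24²/6.4² = 4% to 1.64²/5.4² = 9%, in line with the simulated reduction of 2% to 8% from adding P-APPS to a model with site and C-APPS. The best simulated variance ratio, 0.916, shortens the SD by 1 − √0.916 = 4%. With mild dependence the gain is 0% to 1%; with none there can be a loss of up to 1%.

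**6. Does any conclusion change?**
- Type I error of the planned test was 0.038 to 0.051 in this simulation, and 0.030 to 0.050 in a separate one with 1,500 trials per case.
- Power of the planned test in settings A to D was 0.998 to 1.000.
- In a further run of the same settings (600 trials per cell), adjustment moved the estimate by 0.1 to 1.3 points on average against an SD of 4 to 6. The significance call differed in at most 0.2% of trials, and the robust (HC3) standard error was no smaller than the simple binomial one in any cell.
- Adding P-APPS as a CMH stratum is worse: up to 35 × 2 × 2 = 140 cells. At N = 180 the share of subjects in informative strata falls from 86% to 63%.

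**The case for a change.** The strongest case is the smaller EU set with strong dependence on grade. At N = 180 and 60% to 70% agreement, an imbalance of 10 points or more arises in 14% to 19% of trials. A regulator would see it in the baseline table, and a prespecified adjusted estimate would answer better than a post hoc one, for one paragraph of SAP text. A logistic score test adjusted for both baselines also beat the planned CMH test at N = 180: power 0.931 against 0.865 in one setting, and 0.996 against 0.986 in another.

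The power comparison does not carry the point. The first setting has average rates of (15+30)/2 = 22.5% and (3+8)/2 = 5.5%, a difference of 17 points. At 90 per arm that is below the 19 to 26 points implied by the plan's own power claim. In both settings the logistic test leaves site out, so part of its gain has nothing to do with P-APPS. Where site stays in both models, the variance ratio is 0.916 to 1.012.

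The interpretive argument stands as a preference. A supportive model would be harmless and could help a reader who sees an imbalance. It would not tighten the reported result: its robust interval was 4% to 8% wider at N = 180, and 2% to 6% wider at N = 360, than the normal-approximation interval. In fairness, that simple interval is slightly too narrow in this set-up.

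**Conclusion.** There is no defect. The P-APPS responder bar does depend on baseline grade, and no readable analysis adjusts for it. But a test stratified by the randomisation factors is valid without further covariates, and C-APPS covers part of any P-APPS imbalance to the extent that the two scales agree. The remaining effect is at most 2.5 points per 10 points of imbalance, against an assumed difference of 32 to 33 points, and the significance call changes in at most 0.2% of trials.

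These sizes rest on assumed responder rates by grade, Grade 4 share, C/P agreement, block size and number of EU sites, because the plan's own values are redacted or not given. The validity of the test does not depend on them. Since the parts of the SAP that would hold a covariate-adjusted or additional analysis are blacked out, the plan cannot be said to lack one. It is fair to ask the sponsor whether baseline P-APPS is used there; either answer leaves the planned analysis sound.
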